Sleep study monitoring (polysomnography): The risks during sleep studies are minimal and confined to minor skin irritation from the placement of adhesive electrodes. It is known that participants with sleep disordered breathing and/or severe nocturnal oxygen desaturation are at increased risk for sudden death during sleep from their underlying breathing disorder. Participants' oxygenation will be assessed in these nocturnal recordings and they will be notified if sustained periods of marked hypoxemia ($\text{SaO}_2 < 90\%$) develop. Those with severe nocturnal oxyhemoglobin desaturations and/or recurrent sleep disordered breathing events will be notified of these abnormalities, and their treating Inspire physician will be made aware for an $\text{AHI} \geq 30$ episodes/hr or if the cumulative time spent with an $\text{SaO}_2 < 90\%$ is $\geq 10\%$ of total recording time. Additionally, emergency resuscitative equipment is immediately available in the laboratory. Full-night sleep studies will be conducted by technicians

who are trained not only in basic cardiopulmonary resuscitation but in the analysis of the EEG and ECG which are being continuously monitored throughout the study.

Propofol administration: Propofol will be given intravenously during the sedated sleep procedure under the care of a skilled airway team (anesthesiologist and head & neck surgeon) in a fully-enabled endoscopy suite.

Risks of Propofol (Diprivan®):

- Common: fast or slow heart rate, low blood pressure, burning/stinging or infection at injection site, apnea, rash, and itching.
- Serious, yet rare: seizure.

Pharyngeal manometry and videoendoscopy: This procedure is a minimally invasive outpatient procedure and can be associated with mild discomfort. Two thin nasal catheters and the nasopharyngoscope are passed through one nostril into the pharynx. Passing the scope through the nostril may result in mild nasal irritation or epistaxis as well as minor gagging. Patients usually acclimatize to the sensation within 5 minutes.

Any incidental finding on videoendoscopy will be evaluated, and an official report will be generated and included in the patient's medical record. The subject will be notified of the incidental finding. Depending on the type of incidental finding, referral may be suggested for evaluation by an appropriate physician (e.g., ENT). We will also discuss the incidental finding with the participant so as to alleviate any anxiety that might ensue and inform the participant about clinical resources available to address any clinical concerns about the finding.

Tidal airflow monitoring and nasal pressure alterations: The risks of monitoring tidal airflow with a nasal mask are minimal and consist of claustrophobia. Exposure to alterations nasal pressure applied to the mask are also of minimal risk.

Topical Lidocaine and Oxymetazoline: The risks are minimal since we will inquire beforehand about sensitivity to these agents during surgical time-out as part of standard of care. Subjects may feel an initial slight burning sensation in their nostrils and an urge to swallow.

Lingual Muscle Stimulation: The Inspire device will be tested during wakefulness to determine the tongue protrusion pattern, stimulation level (voltage), electrode configuration, and the respiratory sensing synchrony.

Recruitment and Informed Consent: There is risk that recruitment and consent practices will not comply with standard regulations and may, as a result, compromise the rights and privacy of potential study participants.

The study team will work diligently to ensure study recruitment will be handled with sensitivity and in compliance with all regulations.

Men and women will be recruited from existing or referred clinic patients. All study recruits will be informed of: 1) why the research is being conducted, 2) why they are being contacted, 3) the protocol, and 4) the voluntary nature of their participation. If they are interested in participation in the current protocol, they will be scheduled for a face-to-face encounter in which they will be able

to ask questions about participation in the trial from the research coordinator and/or study doctor.

It will be made clear that all participation in the study is completely voluntary. Informed consent will be obtained in person, after an interview with each participant by the investigators and/or study coordinators responsible for this specific protocol who will fully explain the research protocol, risks and possible benefits. The signed consent form will also contain specific explanations of the possible risks in layman's terms. Patients will have the opportunity to ask questions prior to signing the consent form and will be told that they are under no obligation and may withdraw without compromising their care.

b. Steps taken to minimize the risks:

To minimize risk of confidentiality all data will be stored in a REDCap database and/or on an institutionally secured and managed network drive. Subjects will be assigned a study ID and their data will be attached to that ID.

c. Data Safety and Monitoring Plan:

The plan for collection, description, monitoring, and analysis of adverse events is presented in accordance with guidelines for adverse event reporting to the IRB.

We will use the following definitions and grading scales for monitoring purposes:

Definition of adverse event (AE)/adverse device effect (ADE): any unfavorable and unintended sign (including an abnormal laboratory finding), symptom, or disease temporarily associated with the use of a medical treatment or procedure, regardless of whether it is considered related to the medical treatment or procedure.

Definition of serious adverse event (SAE): any event that is fatal or life-threatening, that is permanently disabling, requires or extends hospitalization of the subject, represents a significant overdose or breach of protocol, suggests that a drug, device, or procedure used in a research protocol has produced a congenital anomaly or cancer, or in the opinion of the investigator, represents other significant hazards or potentially serious harm to the research subject or others.

Definition of unanticipated adverse device effect (UADE): A UADE is any serious adverse effect on health or safety, or any life-threatening problem or death caused by, or associated with, a device, if that effect, problem, or death was not previously identified in nature, severity, or degree of incidence in the investigational plan or application, or any other unanticipated serious problem associated with a device that relates to the rights, safety, or welfare of subjects.

Adverse events will be graded as (a) mild (adverse event of little clinical significance), (b) moderate (adverse event between mild and severe – causing some limitation of usual activities), or (c) severe (an event that results in death, is life-threatening, requires or prolongs hospitalization, causes persistent or significant disability/incapacity, represents a significant overdose or breach of protocol, results in congenital anomalies/birth defects or produces cancer, or in the opinion of the investigator, represents other significant hazards or potentially serious harm to the research subject or others), and their attribution will be classified as (a) not related (clearly not related), (b) possible (may be related), (c) probable (likely related), (d) definite (clearly related), or (e) unable to assess.

The Data Safety and Monitoring Plan for this project is designed in accordance with NIH guidelines published in <http://grants.nih.gov/grants/guide/notice-files/not98-084.html>. Adverse events and

deviations will be reported to the regulatory sponsor, and to IRB as applicable. Serious adverse events will be reported to the regulatory sponsor and to IRB in accordance with institutional reporting requirements. It is our intention to make any serious adverse event known to these entities within 24 hours with follow-up information as it is acquired. Additional safeguards for research subjects will ultimately accrue from our approach to data sharing. Our first approach is the traditional one of publishing results in peer-reviewed scientific journals. The growing use of computerized data repositories in association with scientific publications permits the storage and public access of much more detailed and extensive information than has previously been available, and we plan to make use of such venues. Final versions of these manuscripts will be furnished to the public through the NIH repository for manuscripts in accordance with current policy. (<http://grants.nih.gov/grants/guide/notice-files/NOT-OD-05-045.html>) We also will provide data tables of de-identified data (limited dataset) to other scientists for their independent analyses with completion of a data-use agreement that is compliant with HIPAA guidelines. We will make data from this study public after publication of primary results.

Procedures to Access and Store Research Data: Urgent results and/or incidental findings will be communicated to the patient and sent to the participant's physician. All the data being used for research will be entered into a database by study identification number only. Research charts will be kept in locked cabinets. Access to research information including personal health information will only be provided to study team members.

Data Confidentiality: Data which include identifiable personal health information (PHI) will be collected during patient encounters using REDCap (Research Electronic Data Capture) or managed on the department's institutionally-managed access-restricted shared drive. The REDCap system contains robust data integrity features and as well as nightly backups. It has excellent security and privacy features, with extensive audit logging. REDCap will also be used to store electronically generated data from overnight polysomnography (PSG) and calculated measurements from magnetic resonance imagining (MRI) analysis. Images from the digital morphometrics will be stored on the department's institutionally-managed access-restricted shared drive. The digital images will be deleted one year after participant consent is obtained. Electronic medical records are kept in a secure, password-protected database, and written information is stored in locked file cabinets or file rooms when not attended by study personnel.

PHI will be stored in accordance with HIPAA regulations and local policies and practices. This includes the storage of PHI in locked cabinets or rooms, limited access to secure data areas by certified participating study personnel, password protection for electronic medical records, and explanation of HIPAA regulations on the study consent form. Data such as laboratory studies that are collected as part of this study may be transmitted to the participants' treating physicians with the consent of the participant. Participants are informed in the consent that PHI may also be disclosed for auditing purposes by the FDA or other regulatory bodies and is subject to subpoena. PHI is not transmitted to the coordinating center or central laboratory in that all data is identified only by an anonymous study ID, and other identifying information such as birthdate is not entered into the central study database. Source records that are transmitted to the coordinating center for data quality audits have identifying information redacted.

d. Legal risks such as the risks that would be associated with breach of confidentiality:

Breach of confidentiality would result in unauthorized individuals having access to information about the participant's medical history. Therefore, all research staff selected to participate in this study

are highly qualified and board certified, when applicable. They are all fully aware of HIPAA regulations regarding patient confidentiality. To prevent unauthorized access:

- (1) Data collected will be kept strictly confidential; this information will be used only for completing the study objectives and in an anonymous form for statistical analyses
- (2) All digital files will be stored on a password secured REDCap database and/or on an institutionally secured and managed network drive and restricted to study investigators and associated staff, on a need-to-know basis
- (3) Subject data will be stored with unique identifiers and will be password protected. All computers will require log-on passwords.

9. Benefits

Participant Benefits: No direct benefit to participants is anticipated.

Societal Benefits: This study promises to develop personalized approaches for selecting patients for hypoglossal nerve stimulation therapy for sleep apnea. In characterizing factors linked to enhanced responses in upper airway patency with stimulation, we hope to elucidate impact of lingual stimulation on airway biomechanical properties that mediate improvements in airway patency. The proposed research should help determine the subgroup of patients for whom hypoglossal stimulation is indicated in the future.

Overall Risk-Benefit Analysis: It is possible that patients receiving Inspire therapy are suboptimally treated. This protocol has the potential to identify these patients and may prompt them to consider further evaluation with their Inspire physician.

10. Payment and Remuneration

Volunteers will receive \$150 for completing baseline polysomnography (Assessment #3), \$100 for completing MRI (Assessment #2), and \$150 for completing the DISE (Assessment #4). If they are asked to repeat Assessment # 3, they will be paid an additional \$150.

These volunteers will be compensated \$25 to cover travel expenses. Payment will be issued at the completion of the study, via check or ClinCard, and will be prorated if applicable.

11. Costs

There are no costs to subjects for participation in this study.

12. References

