Patients with implanted hypoglossal nerve stimulation (Inspire[®]) devices will be recruited for this protocol from the University of Pennsylvania or Thomas Jefferson University. All study procedures will be conducted by the clinical research team at the Hospital of the University of Pennsylvania campus (including HUP main, HUP Pavilion and PCAM). Medical records of these referrals will be assessed preemptively or at the time of the clinic or procedure visit for eligibility for this protocol. The patients will be asked whether they are interested in participating in the protocol, at which point informed consent will be obtained for those willing and eligible to enroll. Participants will also

complete a standard MRI screening form to assess eligibility for MRI, including potential claustrophobia.

Design (see Study Flow below)

Participants will initially be consented and screened for this study with a brief medical history and physical exam ([Visit #1](#)). The diagnosis of obstructive sleep apnea may be confirmed from prior sleep study reports. This visit may occur during routine clinical follow-up, if applicable, and may have already been completed prior to study enrollment (primary exception: Thomas Jefferson University patients). Once all inclusion criteria have been met, participants will continue with 3 additional assessments/visits (total 4 visits) per research protocol. In order to facilitate scheduling, these visits may occur in any order:

Eligible participants will undergo upper airway imaging ([Visit #2](#)), where craniofacial morphology will be assessed with MRI measurements and digital morphometric measurements (Study B only).

Participants will then attend an in-lab overnight sleep study ([Visit #3](#)). This will be a full standard polysomnography study where brain activity, body movements, modified EKG, respiratory parameters, and oxygenation will be monitored according to gold standard AASM guidelines. The sleep study will be performed in a split-night fashion including (1) a baseline sleep assessment to measure apnea severity, and (2) hypoglossal nerve stimulation with Inspire to measure response to therapy.

[figure not shown]

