Prior to sleep, patients will undergo facial measurements. A digital camera with laser pointers will be used to capture a series of craniofacial photographs (frontal, profile and neck extended) and intra-oral photographs (junction of the hard and soft palate, airway, or base of tongue). The participant will then perform serial tongue force exercises using a bulb behind their front teeth to assess tongue force.

Thereafter, responses to stimulation will be assessed during DISE with ultrasound measurements of tongue morphology and with measurements of pharyngeal patency during DISE ([Visit #4](#)). Responses in pharyngeal patency will be assessed with video endoscopy, pharyngeal manometry, and tidal airflow monitoring (Studies A+B) while briefly stimulating tongue muscles during DISE (Study B only).

COVID-testing for each of the visits/assessments listed above will be required per departmental guidelines/regulations.

Each of the specific study procedures shown in the Study Design are described immediately below.

Study Flow Diagram

Abbreviations:

- OSA: Obstructive Sleep Apnea
- DISE: Drug-Induced Sleep Endoscopy
- Hx/PE: History/Physical Exam
- HGNS: Hypoglossal Nerve Stimulation

ASSESSMENT #1: CRANIOFACIAL
MRI SCAN (Visit #2)
 • Bony morphology
 • Tongue Size
 • Fat content
 • Pharyngeal lumen size

+

ASSESSMENT #2: OVERNIGHT
SLEEP STUDY (Visit #3)
SPLIT PSG: $\frac{1}{2}$ baseline, $\frac{1}{2}$ HGNS (settings unchanged from clinical optimization)

+

ASSESSMENT #3: DISE STUDY
(Visit #4)
 • Pharyngeal Videoendoscopy
 • Tidal Airflow and CPAP changes
 • Pharyngeal Manometry
 • Submental Ultrasound

	Visit 1: Screening/ Consent*	Visit 2: MRI	Visit 3: Sleep Study*	Visit 4: DISE
Informed Consent	X			
History and Physical	X			
Questionnaires	X			

**Study A (Baseline
Protocol)**

DISE				X
Pharyngeal Manometry				X
Tidal Airflow Monitoring				X
Airflow Manipulation				X
Ultrasound				X

**Study B (Stimulation
Protocol)**

MRI		X		
Digital Morphometrics			X	
Tongue Force			X	
In-Lab Sleep Study			X	
DISE				X

Pharyngeal Manometry				X
Tidal Airflow Monitoring				X
Airflow Manipulation				X
Ultrasound				X
Nerve Stimulation			X	X

*The screening/consent visit may occur during the first scheduled assessment (MRI, PSG, or DISE) to facilitate scheduling and reduce patient burden.

Visit #1: Clinical Evaluation

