1. **Baseline Questionnaires:** Standard screening questionnaires will be administered initially at the time subjects are screened and consented. These questionnaires will assess several demographic, anthropometric, and physical health domains (see attached questionnaires). We will administer the standard Sleep Surgery clinical questionnaire which includes ESS, ISI, FOSQ-10, NOSE, sleep quality, snoring, etc. We will perform an Inspire device download to evaluate study eligibility (therapy compliance), and record their treatment settings. Patients without the most recent Inspire remote will be provided with one.

Visit #2: Overnight Sleep Study, Digital Morphometrics, Tongue Force Assessment

1. **Sleep study monitoring (polysomnography):** Standard monitoring of sleep will occur during Visit #2. For patients opting for Study A only, the sleep study may have already been performed as part of routine clinical care. For Study B, overnight nocturnal recordings will be performed in our sleep laboratory and will follow the same procedures (#1-5) outlined in Visits #3-4 below. The study will include monitoring of EEG, submental EMG, EOG, S_pO_2 , tidal airflow, thoraco-abdominal efforts, and body position. Recordings will be archived on an institutionally secured and managed network drive and accessible only to study personnel. Recordings will be accessed via a HIPAA secured web portal. Patients will be required to wash out from therapy between 5-7 days prior to PSG, i.e. they cannot use HGNS or other therapies during this time. A split night study will be performed (partially with HGNS, partially without). HGNS will not be titrated, i.e. we will use the settings optimized by clinical care prior to study participation. Patients must have a minimum of one hour of supine non-REM stage 2 sleep during both the baseline and treatment (with HGNS) assessments. If patients are unable to meet these criteria, they will not proceed with DISE.

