Participants will temporarily stop all therapy for OSA (particularly Inspire) for 5-7 nights prior to their sleep study. Each participant's medical therapy will continue unaffected by this study with the addition of submental ultrasound examination, MRI, and of one unscheduled polysomnography.

5. Inclusion/Exclusion Criteria

Inclusion Criteria:

- Adult patients (≥ 22 yrs) willing and capable of providing informed consent
- Implanted with the MRI-conditional Inspire hypoglossal nerve stimulator (Model 3028)*
- Compliant with Inspire therapy (> 20 hours/week over 2+ weeks) as a standalone treatment for sleep-disordered breathing
- Inspire Remote Model 2500 or later

Exclusion Criteria:

- MRI contraindications (claustrophobia, ferromagnetic implants/foreign bodies, etc.)*
- Inspire Model 3024
- Inspire Remote Model 3032
- Patients who have fallen asleep while during resulting in an accident or “near miss” accident within 1 year prior to device implantation.
- Inability to sleep in the supine position (by self report)
- History of severe difficulty initiating or maintaining sleep in the laboratory.
- Pregnant women**

* The Inspire model 3028 is not considered an MRI contraindication.

**Women of child bearing potential must undergo a urine pregnancy test (UPT) prior to enrollment. A second UPT is performed prior to DISE as part of routine clinical workup. This study involves temporarily stopping treatment of obstructive sleep apnea, which may harm the fetus.

6. Drugs/Substances/Devices

a. The rationale for choosing the drug and dose or for choosing the device to be used.

We will administer propofol, which is routinely given for DISE procedures. The rationale for choosing this drug is based on its reliability, well-established tolerability, safety, and low muscle-relaxant profile.

Lidocaine jelly (~ 2 mL) will be squirted into each nostril prior to passing the pharyngeal catheter and endoscope.

The protocol will involve recruiting patients already implanted with the Inspire HGNS system. We have selected this device in place of stimulating with custom fine-wire electrodes to reduce patient burden. The Inspire device is safe, well-tolerated, and FDA-approved for treatment for OSA.

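### The consent-visit footnote allows a Study B participant to be consented at a first-scheduled PSG, yet that PSG requires 5-7 nights off OSA therapy beforehand

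*SAP*

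**What the plan says.** **Timing of consent.** The footnote to the schedule table in section 4a reads: "The screening/consent visit may occur during the first scheduled assessment (MRI, PSG, or DISE"). The reasons it gives are easier scheduling and less burden on patients. The Design text in the same section adds, of the three assessments: "In order to facilitate scheduling, these visits may occur in any order". The PSG can therefore come first.

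Other text puts consent at the start. The opening of section 4a has patients asked about their interest, "at which point informed consent will be obtained for those willing and eligible to enroll". The Design text says: "Participants will initially be consented and screened for this study with a brief medical history and physical exam". It lets participants go on to the assessments only when the inclusion criteria are met. Section 8a (Recruitment and Informed Consent) describes consent as given in person after an interview, with no remote route.

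**Washout.** The sleep study procedure in section 4a states: "Patients will be required to wash out from therapy between 5-7 days prior to PSG". Section 4d states: "Participants will temporarily stop all therapy for OSA (particularly Inspire) for 5-7 nights prior to their sleep study". Section 8a (Therapy Washout) gives the same 5-7 nights and limits the washout to Part B.

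**Safeguards during the washout.** Section 8a places driving advice at the consent visit (Visit 1) and adds a check-in call after 2 nights off therapy. Section 7d describes the same call, with a question about falling asleep at the wheel and withdrawal of anyone who says yes.

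**The concern.** The footnote names the PSG as a place where consent may first be obtained, but a Study B PSG can be done as specified only if the patient stopped treatment several nights earlier. Section 4d describes this PSG as an unscheduled addition to the participant's care, so the stop is imposed by the research and is not routine management.

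Section 8a itself says that untreated OSA raises the risk of daytime sleepiness and, through it, of road accidents. It lists the advice at consent and the check-in call among the measures against that risk. If consent comes at the PSG, a patient would take on the research risk before agreeing to the research and before hearing the advice tied to the consent visit.

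**Working it through.** The plan gives no figure to reproduce. The check sets the statements side by side and lays out the timeline, counting the PSG as night 0.

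**Inputs**
- Consent may occur at the first scheduled assessment, PSG included (section 4a, table footnote).
- The assessments may be taken in any order (section 4a, Design).
- Washout of 5-7 days or nights before the PSG (sections 4a, 4d and 8a); Study B only (section 8a).
- Check-in call after 2 nights off therapy (sections 7d and 8a).
- Driving advice at the consent visit (section 8a).
- Consent in person (section 8a).

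**Case 1: consent at a separate Visit 1, or at a first-scheduled MRI or DISE.** Neither the MRI nor the DISE carries this washout. If the washout starts after that visit, the order is consent and advice, treatment stop, call, PSG. There is no conflict.

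**Case 2: consent deferred to a first-scheduled PSG, washout carried out.**
- The washout starts 5 to 7 nights before the PSG.
- With a 5-night washout the call falls 5 − 2 = 3 nights before the PSG. With a 7-night washout it falls 7 − 2 = 5 nights before.
- Consent, screening, the Visit 1 device download that checks therapy compliance, and the section 8a driving advice all fall at night 0.
- The whole treatment stop, the call and the withdrawal rule therefore come before consent.

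**Case 3: consent deferred to a first-scheduled PSG, no washout until consent is given.** The PSG is then recorded without the 5-7 nights off therapy that sections 4a, 4d and 8a require.

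For Study B no further case makes the footnote's PSG option usable. Because section 8a has consent given in person, an earlier remote consent, which the plan does not describe, cannot be assumed to fill the gap.

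**Secondary comparison.** Section 7d advises against driving and the use of heavy machinery throughout the washout. Section 8a advises only against driving while sleepy. Section 7d also gives the washout length in two ways, as 5 days and as 5-7 nights.

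**The case against.** The strongest reply is that the plan plainly intends consent to come first. Participants are consented at the outset, eligibility is settled before the assessments, the washout advice belongs to the consent visit, and a withdrawal rule presupposes someone already enrolled. No text directs a washout before consent. On this view the fault is one over-inclusive word in a permissive scheduling note.

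That is a fair account of the intent, and it limits the weight of the point. It does not remove the conflict. The footnote is the specific permission, it names the PSG, and nothing in the plan says that consent must precede the start of the washout. Section 8a says that interested recruits are told about the protocol and scheduled for a face-to-face meeting, but does not place that meeting before the washout.

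Several stronger readings are tempting and are not supported:
- A reader might infer that the safety call is lost. It is timed from the start of the washout, so it would still fall within it; the difficulty is that it would come before consent.
- A reader might infer that no driving advice could be given in time. Section 7d's advice is not tied to the consent visit; only section 8a's is.
- A reader might infer that PSG-first is common, because the procedure text says "Standard monitoring of sleep will occur during Visit #2" while the schedule table gives Visit 2 to the MRI. Inconsistent visit numbers say nothing about frequency. Nor would counting the permitted visit orders, since PSG-first with an earlier consent visit is harmless.
- A reader might infer that the pregnancy test would also come after the treatment stop. The plan requires it before enrollment but assigns it to no visit.
- A reader might call the two driving texts contradictory. They differ in scope: following section 7d also satisfies section 8a.

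**Conclusion.** The point holds as an internal inconsistency. For Study B, using the footnote's PSG option means either a research treatment stop before consent or a PSG without its required washout. Where the washout is carried out, all 5-7 nights fall before consent.

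This applies only when the PSG is first and consent is deferred to it. How many participants that would be is not stated and cannot be derived from the document. Study A is not affected: section 8a limits the washout to Part B, and the Study Summary records Study A recruitment as complete. The effect is on consent sequence and participant protection. The sample size and the analysis do not depend on it.

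The difference in driving advice and the two statements of washout length are a secondary drafting matter. Which clinical wording should stand is not judged here.

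**What to change.** Amend the schedule footnote so that, for Study B, the screening/consent visit may not first occur at a PSG that requires a prior research washout. Bring it into line with the consent text in section 4a and the washout text in sections 4a, 4d and 8a. The MRI and DISE options can stay, provided any washout starts after consent.

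In the same amendment, reconcile sections 7d and 8a to one driving instruction, and use one statement of the washout length throughout. The sponsor and the investigator should choose the wording.

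The cost is a text amendment and a small loss of scheduling flexibility: an earlier consent contact for participants whose PSG comes first.
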